#### **1.2 Left ventricular assist devices**

Advanced HF is refractory HF in which the disease has progressed despite standard medications to a point where there is a need for cardiac replacement therapies. Approximately 10% of the 3 million patients with HF with reduced left ventricular ejection fraction (HFrEF) in the United States (US) have advanced (end stage or stage D) HF (AHF) and are in need for cardiac replacement therapy or end of life care. Because of the limited supply of cardiac donors (approximately 3273 hearts transplanted in the US in the year 2017) and instability of some transplant candidates awaiting organs, durable left ventricular assist devices (LVADs) have emerged as an alternative or as a bridge to transplantation. Improvement of LVAD technology has revolutionized the field of AHF, with markedly improved survival and quality of life for thousands of individuals compared with medical therapy alone. Hence, the rate of LVAD utilization is steadily growing in the US and worldwide.

However, despite mechanical support of the left ventricle, approximately 50% of the patients die over the course of the 4 years following LVAD implantation. Right ventricular dysfunction and failure frequently occurs in the LVAD population and contributes to the high incidence of re-hospitalization and mortality. Adding to the complexity is the fact that progressive right HF augments susceptibility to developing one or more of the other

[figure not shown]
causes of death in these patients.

Multiple mechanisms are postulated to contribute to right HF after LVAD implantation. Inflammation contributes to progressive myocardial dysfunction in acute myocardial infarction and in chronic HF of ischemic or non-ischemic etiology and inflammatory cytokines are higher in HF patients with LVAD than HF or healthy controls and remain persistently elevated during at least 9 months of follow up

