## **SUBJECT PARTICIPATION**

Eligible participants must have advanced HF of ischemic etiology, defined as 1) a prior history of myocardial infarction and/or 2) angiographically (invasive or cardiac CT angiography) documented significant CAD (defined as a prior history of coronary revascularization (CABG or PCI) and/or obstructive CAD ( $\geq 75\%$  stenosis of the left main or proximal LAD or  $\geq 75\%$  stenosis of two or more major epicardial coronary arteries)) or non-ischemic cardiomyopathy etiology.

Enrollment window will open after discharge from index implant hospitalization and once the patient has been deemed stable with their LVAD implantation.

The screening evaluation will include obtaining written informed consent, collection of a complete medical history, including current and past medications, physical examination and laboratory tests. LVAD implantation is required for inclusion in the study.

A comprehensive 2D and 3D and 3D and Doppler transthoracic echocardiography with speckle tracking and gated blood pool SPECT ventriculography for assessment of right and left ventricular systolic function and volumes will be performed at baseline and at the specific time points during follow-up.

Eligible subjects will receive repeated infusions of either MSCs or placebo based on randomization at time 0 and at day 30 ( $\pm 7$  days) and day 60 ( $\pm 7$  days).

Follow-up visits will occur at days 7 ( $\pm 2$  days), 30 ( $\pm 7$  days), 37 ( $\pm 2$  days), 60 ( $\pm 7$  days), 67 ( $\pm 2$  days), 90 ( $\pm 7$  days), 180 ( $\pm 7$  days), and 360 ( $\pm 7$  days). Information on AEs, concomitant medications, vital signs, clinical laboratory tests and physical examination will be collected according to the schedule of assessments (Appendix A). All guideline-based medical care will continue as prescribed by the subject's personal physician(s). Use of other investigational agents or treatments is not allowed during this study.

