## 4.2 Endpoints

### PRIMARY ENDPOINT

#### **Safety of MSCs assessed at the following time-intervals:**

Baseline and days 30, 60, 90, 180, and 360 post-initial infusion

1. Procedural complications
2. Vital signs
  - a. Temperature
  - b. Mean arterial blood pressure
  - c. Heart rate
  - d. Respiratory rate
  - e. Weight
  - f. LVAD parameters: Pump speed, flow, pulsatility and power
3. Uncontrolled systemic infection.
4. Hemodynamically unstable clinical arrhythmias that require appropriate defibrillator shock, anti-tachycardia pacing or initiation or escalation of antiarrhythmic medications.
5. Laboratory tests
  - a. Complete blood count (CBC)/ differential.
  - b. Comprehensive Metabolic Panel: Sodium, potassium, chloride, bicarbonate, blood urea nitrogen (BUN), creatinine, glucose, calcium, magnesium and liver function tests (ALT, AST, alkaline phosphatase, bilirubin and albumin)
  - c. Troponin-I.
  - d. Allosensitization (change in antibodies against HLA (panel reactive antibody test) from baseline for strong HLA antibody specificities (MFI>2000))
6. Electrocardiogram.
7. All-cause mortality. This will be reviewed by the DSMB. The LVAD population is a high risk group with very

high mortality, which will be taken into account when reviewing safety. Survival rate among HF patients with LVAD is 95% at 1 month, 81% at 1 year, 70% at 2 years, 59% at 3 years and 49% at 4 years. For patients enrolled within our study window, we would expect a 20% mortality rate in our patient population.

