## 5 STUDY ENROLLMENT

Subjects will participate in this study for about 360 days as follows: Patients will be deemed enrolled once the patient is randomized.

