#### INCLUSION CRITERIA

1. Age  $\geq 18$  years.
2. One of the two following HF etiologies:
  - a. Ischemic HF etiology, defined as 1) a prior history of myocardial infarction and/or 2) angiographically or cardiac CTA documented significant CAD (defined as a prior history of coronary revascularization (CABG or PCI) and/or obstructive CAD ( $\geq 75\%$  stenosis of the left main or proximal LAD or  $\geq 75\%$  stenosis of two or

more major epicardial coronary arteries)) prior to LVAD implantation (any coronary angiogram ever prior to LVAD implantation can be used, but an angiogram is not required to confirm non-ischemic etiology, imaging is acceptable).

- b. Non-ischemic cardiomyopathy
3. Advanced HF defined as HF requiring LVAD implantation and deemed stable on his/her LVAD.
4. On stable medical therapy (per the discretion of the treating physician) including beta-blockers, ACE-inhibitors, angiotensin receptors blockers, angiotensin receptor neprilysin inhibitor, mineralocorticoid receptor antagonists, isosorbide, hydralazine, and mineralocorticoid receptor antagonists) and optimized pump speed for at least a month prior to randomization.
5. HS-CRP level  $\geq 2$  mg/l.
6. NYHA class II-III symptoms.
7. Ability to understand and provide signed informed consent.
8. Reasonable expectation that patient will receive standard post-treatment care and attend all scheduled safety follow-up visits.

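### Does the 20% expected mortality in section 4.2, given without a time span or a source, need to be corrected against the survival figures beside it?

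*Combined protocol and SAP*

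**What the plan says.** Item 7 of the primary endpoint in section 4.2 is all-cause mortality, to be reviewed by the DSMB. It describes a population with "high mortality, which will be taken into account when reviewing safety" and then gives a survival curve: "Survival rate among HF patients with LVAD is 95% at 1 month, 81% at 1 year, 70% at 2 years, 59% at 3 years", followed by 49% at 4 years. The next sentence is the one at issue: "For patients enrolled within our study window, we would expect a 20% mortality rate in our patient population". No period and no derivation accompany it.

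Four other places bear on how it should be read:

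- **Time origin of the curve.** Section 1.2 says that "approximately 50% of the patients die over the course of the 4 years following LVAD implantation". This agrees with 49% alive at 4 years, so the curve runs from implantation.
- **Entry.** Under Subject Participation: "Enrollment window will open after discharge from index implant hospitalization and once the patient has been deemed stable with their LVAD implantation". Inclusion criterion 4 also asks for stable therapy and "optimized pump speed for at least a month prior to randomization". No latest time since implantation is set.
- **Follow-up.** Section 5: "Subjects will participate in this study for about 360 days". The primary safety items in section 4.2 are assessed up to day 360.
- **Selection.** Criterion 5 requires raised HS-CRP and criterion 6 requires "NYHA class II-III symptoms". Exclusion criteria 8 and 9 remove transplant candidates and patients with another life-limiting illness.

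**The concern.** A mortality percentage without a period cannot be interpreted on its own, and this is the only numerical expectation the protocol gives for deaths among enrolled patients. The figures beside it seem to contradict it. A curve that starts at implantation includes deaths in the first month, and those patients can never enter the trial. If the 20% is first-year mortality from implantation, rounded up from 19%, it is too high as a background rate for people who have already survived to discharge and stability.

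The direction matters. A safety board working with too high a background rate would be slower to see an excess. Six or more deaths in an arm of 15 has probability 6.1% if the true rate is 20%, but only 1.0% at 13.4% and 2.8% at 16.7%. The same count would look unremarkable on one expectation and unusual on the other.

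**Working it through.** **Inputs.** Survival S = 1, 0.95, 0.81, 0.70, 0.59 and 0.49 at 0, 1, 12, 24, 36 and 48 months (section 4.2, item 7). Follow-up is 360 days, or 11.83 months (section 5). There are 30 patients, 15 per arm (section 4.1). Values between the listed times are interpolated on the log scale; linear interpolation gives the same range.

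**1. Can the 20% be reproduced?** There is no stated formula to follow. From implantation, mortality is 1 − 0.81 = 19.0% at one year and 18.8% at 360 days, and it reaches 20% at about 13.0 months. First-year mortality from implantation is the only one-year reading near 20%.

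**2. Mortality conditional on survival to entry.** For entry at time e, the 360-day mortality is 1 − S(e + 360 d)/S(e). The 12-month version at whole years needs no interpolation.

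| Entry after implant | 12-month mortality | 360-day mortality | Deaths expected in 30 over 360 days |
|---|---|---|---|
| 1 month | 1 − 0.80/0.95 ≈ 15.8% | 15.6% | 4.7 |
| 1 year | 1 − 0.70/0.81 = 13.6% | 13.4% | 4.0 |
| 2 years | 1 − 0.59/0.70 = 15.7% | 15.5% | 4.7 |
| 3 years | 1 − 0.49/0.59 = 16.9% | 16.7% | 5.0 |

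At 20% the expected number is 30 × 0.20 = 6.0, so the gap is 1 to 2 deaths.

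**3. How long until the conditional curve reaches 20%?** Solving S(t) = 0.80 × S(e) gives 494 days for entry at 1 month, 530 days at 1 year and 468 days at 2 years. From 3 years the answer lies beyond the curve, because 0.80 × 0.59 = 0.472 is below 0.49.

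**4. How different would enrolled patients have to be?** The hazard ratio against the curve needed for 20% at 360 days is ln(0.80)/ln(1 − p). It is 1.22 at p = 16.7%, 1.32 at 15.6% and 1.55 at 13.4%.

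**5. How firm is the 13% to 17% range?** The lower entry limit follows from the eligibility rules. The 3-year limit does not: it is the last entry time for which the curve supports a year of follow-up. The listed survivals are whole percentages. Shifting each by half a point in the least and most favourable directions widens the 360-day range to about 12% (entry at 1 year) and 18% (entry at 3 years). It stays below 20%, but 13% to 17% is tighter than the inputs justify.

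**6. Could the trial tell the two apart?** Six deaths in 30 has an exact 95% interval of 7.7% to 38.6%, which covers both figures.

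**7. Where is the 20% used?** Section 9 makes the analysis descriptive. Section 9.2 compares adverse events between arms by Fisher's exact test, which takes no external rate. Section 9.3 bases the sample size on no power calculation. Section 9.4 plans no formal interim efficacy analysis. Sections 5.4 and 8.5 set no mortality threshold. The figure enters no calculation.

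**The case for a change.** The strongest argument for a change is that the remedy costs one sentence and the figure concerns a primary safety item. The 20% is explicitly about enrolled patients, yet the nearest source for it counts deaths that happen before enrolment. Rounding 19% to 20% does not bridge the gap to 13% to 17%. An inflated background rate errs in the unsafe direction.

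Most of this stands as description. The period and source are missing, and the conditional arithmetic is right on its assumptions. What does not follow is that the 20% is wrong. The protocol sets the curve and the expectation side by side without saying that one yields the other. The trial population is not the general LVAD population. Raised HS-CRP is required, and the protocol's own hypothesis ties inflammation to worse outcomes; transplant candidates are excluded. Other criteria, such as the NYHA class range and the exclusion of other life-limiting illness, could lower risk. A hazard 1.22 to 1.55 times that of the curve would suffice for 20%, and nothing in the documents confirms or excludes it.

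Putting 13% to 17% in its place would replace one unsupported figure with another. It would rest on an entry limit the protocol does not have and on the assumption that selected patients follow the general curve.

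The worry about a board being misled is also limited. The full curve stands directly beside the 20%, so the board can condition on survival to entry itself. The concurrent placebo arm (section 9.1) gives a comparison that depends on neither figure, and the board receives all serious adverse events (section 8.5).

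**Conclusion.** No change is needed. The sentence lacks a period and a source, and if the 20% was taken from first-year mortality after implantation, it overstates the background rate on that curve: about 13% to 17% over 360 days, or 4 to 5 deaths in 30 rather than 6. That comparison assumes entry between 1 month and 3 years after implantation and patients who follow the general LVAD curve. Entry later than 3 years cannot be checked. The documents do not show that 20% is wrong for this selected group.

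The intended period can be read from the context: item 7 is assessed to day 360 and participation lasts about 360 days. The figure is a background remark that feeds no decision rule, test or sample size. Stating its period and source would be tidier drafting, but following the plan as written gives the same results and the same conclusions.

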#### **5.4 Study Termination**

The Sponsor has the right to terminate the study at any time. Reasons for terminating the study may include, but are not limited to, the following:

- The incidence or severity of AEs in this or other studies indicates a potential health hazard to subjects.
- Unsatisfactory subject enrollment.
- Rate of enrollment of < one subject per 3 months.
- An excess drop out of subjects (a total of  $\geq 5$  subjects per each arm, but not due to VAD –related mortality).
- Inaccurate or incomplete data recording.
  - $\geq 20\%$  missing data for the primary safety endpoints.
  - $\geq 30\%$  missing data for the efficacy endpoints.

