## **9 STATISTICAL CONSIDERATIONS**

Statistical analyses will be descriptive. Summary statistics will consist of sample size (N), means, standard deviations, medians, and minimum and maximum values for continuous variables, and counts and percentages for categorical variables. Tables will summarize all safety and efficacy outcome measures by actual treatment received. Summary tables will indicate the number of subjects with complete data for each measurement, event or outcome. No substitutions will be made for missing data. All analyses will be based on available data.

A detailed Statistical Analysis Plan will be written prior to data analysis. Significant deviations from the original statistical analysis plan will be detailed in the final study report.

This study intentionally is not powered and will enrolled 30 patients with 15 in each of the two randomization arms.

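### Does the plan's own expected mortality of 20% meet its termination reason of 20% or more missing primary safety data?

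*Combined protocol and SAP*

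**What the plan says.** Section 4.2 makes safety the primary endpoint, assessed at "Baseline and days 30, 60, 90, 180, and 360 post-initial infusion". It has seven items: procedural complications, vital signs with LVAD parameters, uncontrolled systemic infection, unstable arrhythmias, laboratory tests (including HLA antibodies), ECG, and all-cause mortality. Under the last it gives general LVAD survival (95% at 1 month, 81% at 1 year, 70%, 59% and 49% at 2, 3 and 4 years) and then states: "For patients enrolled within our study window, we would expect a 20% mortality rate in our patient population". No time horizon is attached to the 20%. Section 5 puts participation at about 360 days.

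Section 5.4 opens its list with "Reasons for terminating the study may include, but are not limited to, the following". One entry is drop-out of 5 or more subjects per arm, with the qualifier "but not due to VAD –related mortality". The next entry is "Inaccurate or incomplete data recording", and beneath it, as a sub-item, stands 20% or more "missing data for the primary safety endpoints". That sub-item names no denominator and no time point, and does not mention deaths.

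Section 9 makes the analysis descriptive, on available data and without imputation, and adds: "Summary tables will indicate the number of subjects with complete data for each measurement, event or outcome". It defers detail to a statistical analysis plan to be written before data analysis.

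**The concern.** The expected death rate and the missing-data threshold are the same number. A subject who has died has no day-360 vital signs, laboratory tests, HLA result or ECG. If those count as missing, a trial that ran exactly as expected would sit on a listed reason for ending it, with no fault in recording. The drop-out entry just above exempts some deaths, which makes the lack of an exemption here look like an oversight. The choices left open (deaths in or out, per visit or pooled, and when) move the chance that mortality alone meets the criterion from 0 to about 0.6. The sponsor could therefore settle the meaning of a numeric reason for stopping after the deaths are known, possibly while enrolment is still open.

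**Working it through.** **Inputs.** 30 subjects, 15 per arm (Section 9); expected mortality 20%, survival figures and visit days (Section 4.2); threshold 20% (Section 5.4).

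**The plan's 20%.** 1 − 0.81 = 0.19 at one year from implant, close to the stated 20%. Subjects enter later, after discharge and once stable. Twelve-month mortality given survival to entry, 1 − S(t+12)/S(t), runs from 1 − 0.70/0.81 = 13.6% (entry at month 12) to 1 − 0.49/0.59 = 16.9% (entry at month 36), for entry anywhere from month 1 to month 36. The 20% is therefore slightly high as a 360-day figure, though usable.

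**Reading A: deaths count, per visit, day 360.** Expected deaths 0.20 × 30 = 6; threshold 0.20 × 30 = 6. With X binomial:

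| Subjects at day 360 | Mortality | Event | Probability |
|---|---|---|---|
| 30 | 20% | X ≥ 6 | 0.572 |
| 30 | 19% | X ≥ 6 | 0.517 |
| 30 | 16.9% | X ≥ 6 | 0.397 |
| 30 | 13.6% | X ≥ 6 | 0.216 |
| 10 | 20% | X ≥ 2 | 0.624 |

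Suppose a further 5% or 10% of survivors miss the visit (an assumption). Missingness is then 0.20 + 0.80 × 0.05 = 0.24 or 0.20 + 0.80 × 0.10 = 0.28, and the chance of 6 or more of 30 is 0.760 or 0.884. The same 5% or 10% without deaths gives 0.003 or 0.073.

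Two cautions apply. A binomial count whose mean is a whole number reaches that mean with probability of at least one half, so 0.572 says little more than that both numbers are 20%. And with 10 subjects the rule is easily met in any case: 10% ordinary missingness and no deaths gives P(X ≥ 2 of 10) = 0.26.

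**Reading B: deaths count, earlier visits.** With a constant hazard giving 20% at day 360 (an assumption), the share dead by day t is 1 − 0.80^(t/360): 1.8%, 3.7%, 5.4%, 10.6% and 20.0% at days 30, 60, 90, 180 and 360. The chance of 6 or more deaths among 30 is 0.005 by day 90 and 0.09 by day 180.

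**Reading C: deaths count, pooled over the five post-baseline visits.** Mean missing = (1.8 + 3.7 + 5.4 + 10.6 + 20.0)/5 = 8.3%. By simulation, the chance that the pooled share reaches 20% is about 0.005. With a curve through the plan's own 1-month and 1-year survival instead, the mean is 9.9%.

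**Reading D: deaths excluded.** Mortality contributes 0.

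**Which reading the text supports.** The threshold is a sub-item of "Inaccurate or incomplete data recording". An ECG that was never due because the subject had died is not a failure of recording. Loss of subjects has its own entry directly above, which is where an exemption for mortality belongs. Of the seven primary items, mortality is fully observed when a subject dies, and procedural complications, infections and arrhythmias are known up to death; only the visit-based measurements stop. Section 5.4 also speaks of the primary safety endpoints in the plural, which fits a pooled share at least as well as a single-visit one. The text points to Reading D, with C next.

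**The case for a change.** The best case for a change is that the authors plainly saw that deaths could meet a termination criterion, wrote an exemption for drop-out, and wrote none here. Even that exemption covers only VAD-related deaths, so it does not settle what happens to the others. Discretion makes a prior definition more useful, since otherwise the reading is chosen with the deaths in view. Nor need the matter wait for the end of the trial: Section 5.4 lists "Rate of enrollment of < one subject per 3 months" as a reason to stop, so enrolment at one subject per 3 months is tolerated, and early entrants could finish day 360 before later ones are randomised. The remedy is a few sentences.

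Some of this stands. The text is silent on deaths, on the denominator and on timing, and a clarifying sentence would do no harm. The rest carries less weight. Enrolment at that slowest pace would take 30 × 3 = 90 months, or 7.5 years; no actual rate is given. The full-cohort count of 6 of 30 at day 360 is known only when follow-up is over and little is left to stop. A definition would not bind the sponsor either, because Section 5.4 lets it terminate at any time and the list is open-ended.

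**Conclusion.** No change is needed. The coincidence of the two 20% figures is real and the arithmetic is right, but the conflict arises only if deaths count as missing, the share is taken per visit at day 360, and the undated 20% is a 360-day figure. Then the chance is 0.57, or 0.22 to 0.40 with mortality derived from the plan's own survival figures. Pooled over visits it is about 0.005 under a constant hazard; with deaths excluded, as the placing of the criterion suggests, it is 0.

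Nothing downstream depends on the choice. Under Section 9 the results are descriptive summaries of available data with the number of complete observations shown, so no estimate or error rate changes. The DSMB reviews all-cause mortality (Section 4.2) and determines whether enrolment continues (Section 8.5), and Section 4.2 says the high background mortality will be taken into account. A sponsor applying the criterion would sensibly count assessments due in subjects still alive and report deaths under the mortality item. Saying so in Section 5.4, and dating the 20% in Section 4.2, would be an optional tidying of wording.
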